## 3.2.19 *Pharmacokinetics, biodistribution and dosimetry analyses*

### 3.2.19.1 *Analysis methods*

#### 3.2.19.1.1 *Descriptive statistics and listings*

The Ipsen requirements for “Clinical PK and Pharmacometrics” instruction CCI will be followed.

Listings of all parameters will be sorted by treatment group, subject, cycle (if applicable) and measurement time during core trial and additional cycles separately.

Descriptive summaries by treatment group and by cycle (if applicable), during core trial and additional cycles separately, will include arithmetic means, Standard Deviation (SD), Coefficient of Variation (CV%), geometric mean, geometric CV%, median, minimum, maximum, n and missing. Descriptive statistics should be displayed only if at least 2/3 of the data are available (not missing) and only if at least 2/3 of the parameters are accurately determined (unflagged); otherwise, only minimum and maximum are reported.

Of note, all BLQ (Below the Limit of Quantification) values must be replaced by missing/zero to compute descriptive statistics according to the rule set below:

- For plasma 3BP-227 concentrations, BLQ data must be substituted by 0 for concentrations measured before the first quantifiable concentration. Any embedded BLQ value (i.e. single BLQ value occurring between 2 quantifiable concentrations) and BLQ values following the last quantifiable concentration in a profile will be set to missing for the purposes of PK analysis. BLQ values substituted by 0 are included in the NCA calculation whereas missing values are ignored. In any case, when all concentrations from a concentration-time profile are BLQ, they must be substituted by 0 and included in the PK analysis dataset.
- For urine 3BP-227 concentrations, BLQ data have to be set as 0.
- No BLQ values are expected for Lu-3BP-227 blood and urine total activity concentrations.
- For biodistribution, the following nomenclature will be used:
  - “NA” (not applicable) for regions that are outside of the field of view (FOV) or for sex-specific organs: to be considered as missing.

- “NC” (not calculable) for regions inside the FOV, but where quantification is not possible or regions without segmentation: to be considered as missing.
- “AU” (absent uptake) for regions inside the FOV, but with no radiopharmaceutical uptake: to be considered as zero.

All BLQ concentrations or missing data will be labelled as such in the concentration data listings.

BLQ values substituted by 0 are included in the calculation of descriptive statistics whereas missing values are ignored.

### 3.2.19.1.2 *Graphical representations*

All BLQ values for 3BP-227 concentrations must be replaced by missing/zero for graphical representation according to the rule set below:

- For plasma 3BP-227 concentrations, BLQ data must be substituted by 0 for concentrations measured before the first quantifiable concentration, and missing for BLQ concentrations after the last quantifiable concentration. Any embedded BLQ value (i.e. single BLQ value occurring between 2 quantifiable concentrations) and BLQ values following the last quantifiable concentration in a profile will be set to missing;
- For urine 3BP-227 concentrations, BLQ data have to be set as missing.

Nominal times are to be used to display the concentration plots.

The graphic representation of PK parameters will be made only if at least 2/3 of the parameters are accurately determined.

### 3.2.19.2 *Analyses on blood pharmacokinetics of Lu-3BP-227*

Blood total activity concentrations (including PK blood sampling dates and times) and blood PK parameters will be listed and summarised as described in section 3.2.19.1.1. A summary will be also planned for both cycles of core trial.

The individual blood total activity concentration-time profiles of Lu-3BP-227 will be presented graphically on linear and log/linear coordinates with both cycles on the same graph, during core trial only. Spaghetti plots (overlay of individual concentration-time profile) will also be reported by treatment group, with both cycles on the same graph, during core trial only.

Graph of arithmetic mean ( $\pm$ SD) on linear and log/linear coordinates will be presented by cycle, with all treatment groups on the same graph, during core trial only.

Scatter plots will be also presented for the  $AUC_{0-t_{last}}$  and  $t_{1/2}$  with all treatment groups on the same graph for cycle 1 and for both cycles.

### 3.2.19.3 *Analyses on urine pharmacokinetics of Lu-3BP-227*

Urine total activity concentrations (including PK urine sampling dates and times) will be listed, amount of drug excreted in urine will be summarised by time interval and overall and urine PK parameters will be listed and summarised at cycle 1 as described in section 3.2.19.1.1.

Individual cumulative urine recovered activity versus time profiles of Lu-3BP-227 will be presented graphically at cycle 1 for each treatment group with all subjects on the same graph.

The graph of cumulative recovered activity in urine over time will be provided for urine total activity concentration of  $^{177}\text{Lu}$ -3BP-227 at cycle 1 with all treatment groups on the same graph.

#### 3.2.19.4 *Analyses on plasma pharmacokinetics of 3BP-227*

Plasma concentrations (including PK plasma sampling dates and times) and plasma PK parameters will be listed and summarised at cycle 1 as described in section 3.2.19.1.1.

The individual plasma concentration-time profiles of 3BP-227 will be presented at cycle 1 graphically on linear and log/linear coordinates. Spaghetti plots (overlay of individual concentration-time profile) will also be reported by treatment group.

Graph of arithmetic mean ( $\pm$ SD) on linear and log/linear coordinates will be presented at cycle 1 with all treatment groups on the same graph.

Scatter plots will be also presented for  $\text{AUC}_{0-\text{tlast}}$  and  $\text{AUC}_{0-\text{inf}}$  with all treatment groups on the same graph for cycle 1 and for both cycles.

#### 3.2.19.5 *Analyses on urine pharmacokinetics of 3BP-227*

Urine total activity concentrations (including PK urine sampling dates and times) will be listed, cumulative amount of drug excreted in urine will be summarised by time interval and overall and urine PK parameters will be listed and summarised at cycle 1 as described in section 3.2.19.1.1.

Individual urine cumulative recovered amount versus time profiles of 3BP-227 will be presented graphically at cycle 1 for each treatment group with all subjects on the same graph.

The graph of urine cumulative recovered amount ( $A_e$ ) over time will be provided for urine concentration of 3BP-227 at cycle 1 with all treatment groups on the same graph.

#### 3.2.19.6 *Biodistribution analysis for $^{177}\text{Lu}$ -3BP-227*

Uptake activity (including assessment dates and times) and PK parameters for organs of interest (healthy liver, bone marrow, left kidney, right kidney, spleen and body) will be listed and summarised as described in section 3.2.19.1.1. PK parameters for target lesions will be summarised similarly. A summary will be also planned for both cycles of core trial for organs.

#### 3.2.19.7 *Radiation dosimetry analysis of $^{177}\text{Lu}$ -3BP-227*

A frequency table on the organ receiving the highest absorbed dose will be provided by cycle and treatment group, for core trial and additional cycles separately, using the results from image-based analysis.

The specific absorbed dose per organ will be summarised by cycle and overall (only for core trial), by treatment group and overall, for core trial and additional cycles separately, using the results from image-based analysis and model-based analysis.

The specific absorbed dose to the target lesions will be summarised for core trial and additional cycles separately using the results from image-based analysis, by treatment group and overall as follows:

- by localisation and overall and by cycle (only for core trial) and on overall cycles,
- by localisation and overall and by study disease, on overall cycles only.

The absorbed organ dose per organ and to the target lesions on cycle 1 and cumulative absorbed dose on cycles 1 and 2 will be analysed by treatment group for core trial using the results from image-based analysis.

The effective dose and specific effective dose will be summarised by cycle and overall (only for core trial) and by treatment group, for core trial and additional cycles separately, using the results from model-based analysis.

Both image-based and model-based analyses will be listed by treatment group, subject and cycle, for core trial and additional cycles separately.

Timing of planar scintigraphy and SPECT/CT assessments will be also listed by treatment group, subject and cycle, for core trial and additional cycles separately.

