1.3.4 Biodistribution and Dosimetry of Radiolabelled 3BP-227

The specificity of 3BP-227 accumulation in NTSR1-expressing tumours in vivo was demonstrated in biodistribution studies in mouse xenograft models with both ¹¹¹In-3BP-227 and ¹⁷⁷Lu-3BP-227. Besides NTSR1-expressing tumours, the uptake of radioactivity in the organs was very low, including the kidneys and the liver. It was shown that 3BP-227 did not penetrate the blood brain barrier. ¹⁷⁷Lu-3BP-227 showed a favourable biodistribution profile exhibiting a good tumour uptake associated with a low uptake in normal tissue and a persistent tumour uptake leading to favourable tumour-to-kidney activity ratio.

In rats, the biodistribution profiles and the effective radioactive doses of ¹¹¹In-3BP-227 and ¹⁷⁷Lu-3BP-227 were comparable. The radioactivity was rapidly cleared from the bloodstream. Tissue concentrations were low. Elimination of radioactivity was primarily through the urine and to a lesser extent via the faeces.

In a biodistribution and dosimetry study of ¹⁷⁷Lu-3BP-227 in Beagle dogs, the radioactivity was rapidly cleared from the blood. ¹⁷⁷Lu-3BP-227 was predominantly and rapidly excreted through the urinary tract with a secondary elimination route via the liver into the gastrointestinal (GI) tract. The main uptake of radioactivity in organs was observed at 2 and 6 hours after injection in muscles, intestines, bones and bone marrow, liver, lungs and kidneys. At 72 hours post injection, all tissues exhibited less than 1% of the injected dose. The highest absorbed dose coefficients were observed in the urinary bladder wall, the large intestinal wall and the kidneys.

Table 1 below summarises the extrapolation of the organ exposure results from these two studies to humans. The extrapolation to humans was performed using a mass-based extrapolation in which the concentration in the animal organs was converted to a concentration in human organs by multiplying the animal concentration by a ratio of the total body weight of the animals and humans [1]. The dosimetry studies in rats and dogs identified as target organs of special interest: urinary bladder, large intestinal wall, kidneys and osteogenic cells.

From the extrapolation of animal data to human, the expected radiation exposure in human study is acceptable.

1.19 - 1.27

0.02 - 0.02

0.03 - 0.10

Compound	¹⁷⁷ Lu-3BP-227	¹¹¹ In-3BP-227	¹⁷⁷ Lu-3BP-227
Species	Rat	Rat	Dog
Specific activity	1.2 to 2.4 mCi/nmol	1.2 to 2.4 mCi/nmol	9.9 MBq/μg

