1.8 Known and Potential Risks to Human Subjects

This is the FIH study conducted with ¹⁷⁷Lu-3BP-227 under controlled conditions. The study will primarily evaluate the safety and tolerability of ¹⁷⁷Lu-3BP-227 but also its potential antitumour effect in subjects with advanced cancers expressing NTSR1. With the exception of an individual clinical treatment use (see Section 1.4), ¹⁷⁷Lu-3BP-227 has never been tested in humans, but has shown no relevant toxicological effects in the animal studies conducted with high safety margins. However, it cannot be ruled out that ¹⁷⁷Lu-3BP-227 could have adverse effects in the human population, which have not been detected in animal studies.

As this is the FIH study, the function of organs identified at risk will be checked as part the of exclusion criteria. Based on the current level of knowledge, those organs are bone marrow, kidney, large intestine, liver and urinary bladder. In conventional fractionated external radiotherapy, the experience is that an absorbed dose of 23 Gy to the kidney gives a 5% expected risk of nephrotoxicity within 5 years [28, 29, 30]. For the bone marrow, a maximum absorbed dose (MAD) of 2 Gy gives approximately a 2% risk of developing leukaemia as a long-term toxicity. In this study, the well-established 2 Gy for the bone marrow MAD and the more conservative approach with 23 Gy as MAD for the kidney will be applied.

Safety measures have been taken into consideration to minimise the risk. Each subject recruited across the sites may be hospitalised for 24 hours following administration for observation at the discretion of the investigator. The level of radioactivity will be monitored until it has fallen to safe levels for discharge, to protect medical personnel and relatives. Depending on the local

regulation, the subject will be hospitalised either in the nuclear medicine or regular oncology ward.

The participating subjects will be closely monitored during the study and during the long-term follow-up period until lost to follow-up, withdrawal of consent, death or a maximum of 5 years, whichever occurs first. Subjects may be withdrawn from the study at any time, if judged to be in their best interest by the investigator or upon the subject's wish. The study will be carried out in specialised clinical centres with nuclear medicine and medical oncology specialists.

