### 3.1.3.3 Radiation dosimetry endpoints for $^{177}\text{Lu}$ -3BP-227

The following parameters will be evaluated (only in organs and target lesions showing uptake):

- Organs receiving the highest absorbed dose by cycle;
- Specific absorbed dose to the target lesions (Gy/GBq) by cycle;
- Specific absorbed dose per organ (Gy/GBq) by cycle;
- Time-Integrated Activity Coefficient (TIAC) (or residence time) per organ and to the target lesions by cycle;
- Whole body effective dose (Sv)
- Whole body effective dose per administered activity (Sv/GBq)
- Absorbed doses on cycle 1 and cumulative absorbed doses on cycles 1 and cycle 2 per organ and to the target lesions (Gy).

The absorbed dose to the target lesions and discernible organs (i.e. organs showing uptake) will be evaluated by image-based analysis. It relies on the visual identification of the regions of interest on the images and determination of activity and absorbed doses using Planet Dose solution (Dosisoft). The organs considered for  $^{177}\text{Lu}$ -3BP-227 image based dosimetry assessment will be the following: Healthy Liver, Total Liver, Bone marrow, Left Kidney, Right Kidney, Intestine (large & small), Spleen, Pancreas, Stomach wall, Right ovary, Left ovary, Uterus, Right testis, Left testis, Thymus, Right thyroid gland, Left thyroid gland, Prostate gland and total body. Additional organs may be added later on.

In addition to the image-based analysis, the absorbed doses of all organs will be evaluated by model-based analysis (OLINDA/EXM version 1.0) using TIAC estimates from the image-based analysis.

Effective dose will be evaluated by model-based analysis.

Finally, absorbed dose in red marrow will also be computed assuming proportionality on activity measures in blood samples (blood based method).

Absorbed doses and specific absorbed doses will be also presented on kidney (left+right) using the average of left kidney and right kidney.

Details on the different calculations are provided in the Dosimetry Analysis Plan of the study.

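### The highest-dose-organ table rests on image-based results only, and the organs named for imaging leave out urinary bladder and osteogenic cells

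*SAP*

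**What the plan says.** Protocol 4.4.2.1 lists the highest absorbed dose among the Phase I dosimetry endpoints, and Protocol 12.2.6.2 asks for the organs that receive it. SAP 3.2.19.7 turns this into a table: "A frequency table on the organ receiving the highest absorbed dose will be provided by cycle and treatment group". The core trial is kept apart from the additional cycles, and image-based analysis is the only source given for the table.

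SAP 3.1.3.3 names the organs for image-based dosimetry: "Healthy Liver, Total Liver, Bone marrow, Left Kidney, Right Kidney, Intestine (large & small), Spleen, Pancreas, Stomach wall, Right ovary, Left ovary, Uterus", and then "Right testis, Left testis, Thymus, Right thyroid gland, Left thyroid gland, Prostate gland and total body". It adds: "Additional organs may be added later on". The same section says that all organs will also be assessed with a model (OLINDA/EXM), which takes its time-integrated activity coefficients from the image-based analysis. It refers to the Dosimetry Analysis Plan for the calculations.

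Protocol 1.3.4 draws four organs of special interest from the rat and dog studies: kidneys, large intestinal wall, osteogenic cells and urinary bladder. For dogs it states: "The highest absorbed dose coefficients were observed in the urinary bladder wall, the large intestinal wall and the kidneys". Protocol 1.8, on organs at risk, says: "Based on the current level of knowledge, those organs are bone marrow, kidney, large intestine, liver and urinary bladder".

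**The concern.** A table that names the organ with the highest dose can only choose among the organs it was given. Two of the four organs that the sponsor's own animal work pointed to are not among those named. Protocol 1.3.4 describes excretion as mainly urinary, so the bladder is an obvious candidate for the top place. If the list is used as printed, the table may report intestine, kidney or another listed organ as the highest-dose organ in subjects whose bladder wall or bone surface received more. What is at stake is the correct reporting of one secondary dosimetry endpoint in a first-in-human radiopharmaceutical trial.

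**Working it through.** **Coverage.** Of the four organs of special interest in Protocol 1.3.4, the image-based list has two (kidneys, and large intestine within its intestine entry). It lacks urinary bladder and osteogenic cells.

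**Check of units.** Protocol 1.6 predicts 0.8 Gy to bone marrow and 1.4 Gy to kidneys at 5 GBq. Table 1 is in mSv/MBq, which equals Sv/GBq and is taken here as Gy/GBq. With the larger sex-specific value in the ¹⁷⁷Lu rat column, dose = coefficient × activity:

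- red marrow: 0.160 × 5 = 0.80 Gy
- kidney: 0.280 × 5 = 1.40 Gy

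Both stated figures are reproduced, so the table is being read on the protocol's own scale.

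**Ranking within each Table 1 column.** Ratio = highest value overall ÷ highest value among organs on the SAP list.

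| Column | Highest overall | Highest on the list | Ratio |
|---|---|---|---|
| Rat ¹⁷⁷Lu, M | osteogenic cells 0.65 | lower large intestine (LLI) wall 0.45 | 1.44 |
| Rat ¹⁷⁷Lu, F | osteogenic cells 0.54 | LLI wall 0.53 | 1.02 |
| Rat ¹¹¹In, M | osteogenic cells 0.26 | LLI wall 0.19 | 1.37 |
| Rat ¹¹¹In, F | osteogenic cells 0.33 | kidney 0.25 | 1.32 |
| Dog ¹⁷⁷Lu, M | bladder wall (assumed row) 1.19 | LLI wall 0.30 | 3.97 |
| Dog ¹⁷⁷Lu, F | bladder wall (assumed row) 1.27 | uterus 0.19 | 6.68 |

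At 5 GBq the ¹⁷⁷Lu values become 3.25 against 2.25 Gy (rat M), 2.70 against 2.65 Gy (rat F), 5.95 against 1.50 Gy (dog M) and 6.35 against 0.95 Gy (dog F).

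**The unlabelled row.** Some Table 1 rows lost their labels when the PDF was read. The row with 1.19 and 1.27 is assumed to be dog bladder wall. No labelled row is bladder, the text puts bladder wall among the highest dog values, and these are the largest dog figures. The matching rat values are read as 0.430 and 0.400 (¹⁷⁷Lu) and 0.240 and 0.320 (¹¹¹In), all below osteogenic cells. If those two rat pairs belong the other way round, the top structure in the ¹¹¹In columns becomes the assumed bladder row, which is also off the list. If the row is set aside altogether, the four rat results stand. The dog case then rests on the sentence in Protocol 1.3.4, because the highest labelled dog rows are on the list.

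**The case against.** The strongest reply is that the list is not closed. SAP 3.1.3.3 allows organs to be added, Protocol 12.2.6.2 has high-uptake organs identified visually and restricts the calculations to organs showing uptake, and Protocol 1.8 promises monitoring of the other organs at risk. An image-based table fits that approach. This stands to the extent that a reader who infers that bladder and osteogenic cells can never appear goes too far. But the clause names no organ and gives no criterion for adding one.

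A second reply is that these doses are reported anyway. The model covers all organs, and its results enter the specific absorbed dose summary and the listings. That also stands, but it does not make the two organs eligible for this table.

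A third is that the omission is less lopsided than it looks. Large intestine and kidneys, both predicted high-dose organs, are on the list. Osteogenic cells and LLI wall nearly tie in female ¹⁷⁷Lu rats, and Protocol 1.8 does not name osteogenic cells as at risk. All of this is correct, so it would be wrong to say that the list misses the high-dose organs as a group.

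Finally, a reader might infer that the modelled bladder dose will be too low, because its inputs come from an image list without a bladder region. The documents do not establish this. Protocol 12.2.6.2 says that renally excreted activity feeds the dosimetry, and the Dosimetry Analysis Plan, which would settle the point, is not available.

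**Conclusion.** The point holds in a limited form. As printed, the table draws on a named list that omits two of the protocol's four organs of special interest, and unless organs are added it may name the wrong organ. In the animal extrapolation the leading structure is off the list in six of six columns. The margin is small in rats (1.02 to 1.44). In dogs it is about 4.0 and 6.7, on the assumption that the unlabelled row is bladder wall. For female dogs the right comparator is uterus at 0.19, not LLI wall at 0.16; using the latter would overstate the ratio.

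The consequence is confined to reporting. The table is descriptive, and the individual discontinuation limits in Protocol 4.7.1 concern kidney, bone marrow and liver, all of which are on the list. A reader might infer a gap in those dosing limits, and the documents give no ground for that. Any underestimate of the modelled bladder dose remains conditional on the Dosimetry Analysis Plan. The change is worth making because the endpoint is pre-specified and the correction is cheap.

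**What to change.** In SAP 3.2.19.7, base the table on the combined image-based and model-based all-organ results, or add a second version from the model-based results, so that bladder wall and osteogenic cells are eligible.

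In SAP 3.1.3.3, name urinary bladder as a source and target region, and confirm in the Dosimetry Analysis Plan that bladder contents enter the model. The two changes belong together, because the model takes its inputs from the image-based analysis. The bladder estimate can use the planned images at every cycle with full imaging (Cycles 1 and 2, and the first and third additional administrations, Protocol 9.2). Urine activity data can support it at Cycle 1 only, and only to 6 hours after the end of infusion at US sites (Protocol 9.1.2).

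The cost is SAP and Dosimetry Analysis Plan wording and one more region to segment, with no new scans, samples or subjects. The bladder estimate will be less certain after Cycle 1, and a footnote to the table should say so.

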### **3.2.20 Exploratory analyses**

Exploratory analyses will be described in a dedicated SAP.

### **3.2.21 Derived data**

The derived data are variables which are calculated from the raw data in the eCRF and not included in the database and will be included in the listings (see [Appendix 1](#)).

